Consent Procedures: All study procedures will be described in detail for the subjects by the research nurse, a physician, or other trained staff person in an individual consent session. The consent form and session will include the following information: Detailed information about the medication; that is, a description of the medication, rationale for why it is being studied, frequency of dosing and length of treatment, potential side effects, safeguards and emergency procedures. Information will also be provided about the psychosocial treatment, frequency of visits and length of treatment, safeguards and emergency procedures, etc. Collection of lab specimens (number of venipunctures and urine specimens required) will be reviewed. Eligibility will be reviewed. The number and frequency of the research interviews and self-assessments will be reviewed. In addition, subjects will be assured that their participation is voluntary and that withdrawal from the study does not jeopardize current or future treatment. Subjects will also be told that if at any time during the study the research team feels that the subject needs more intensive, standard treatment, the subject will be referred to one of the available inpatient or outpatient treatment programs near their place of residence.

All subjects will be informed of potential risks and benefits involved in the study. Potential medication side effects will be described to all subjects. Subjects will be informed that their participation in the treatment trial may be discontinued at any time because of serious medication side effects, their noncompliance with treatment, missing appointments or if continued participation is considered an endangerment to their welfare.

At the end of the consent session, a quiz is given. Subjects scoring below 100% correct will receive additional instruction regarding the study and consent form. Incorrect questions from the quiz will be administered again until all questions are answered correctly.

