Protection of Subjects: Potential subjects will be screened for medical illnesses that would preclude the use of varenicline. Subjects selected for the study will be monitored closely. Subjects will be evaluated three times a week while receiving study medication. Adverse events will be monitored by research staff at weekly visits, and the psychiatrist or nurse will be available at other visits to assess the subject if needed. At the conclusion of medications, an end of study physical will be completed and the baseline laboratory tests, including EKG, will be repeated. Subjects will be given a 24 hour emergency number they can call if necessary. Adverse events: If the subject is discontinued in treatment due to a serious adverse event, the subject will be followed clinically by medical staff until the adverse experience resolves itself and becomes stable. Subjects taking concomitant medications will be monitored closely for signs of toxicity. Subjects with a history of current severe psychiatric symptoms, use of any investigational medication within the last 30 days, AIDS or other serious illness which may require hospitalization during the study, impaired renal function or known liver disease, will be excluded from the study. Pregnant women or women who refuse to use acceptable forms of birth control will be excluded from the study. Urine pregnancy tests will be performed monthly.

The dose of varenicline will be started at 0.5 mg BID and increased to 1.0 mg BID by the end of the first week of medication therapy.

Venipuncture will be carried out with good aseptic technique by a nurse or physician. Venipuncture sites will be monitored carefully for signs of infection.

If a subject experiences an adverse event, appropriate evaluation and management will be undertaken. This may include medical management, a reduction in study of medication, a temporary cessation of study drug, or early termination from the trial, if necessary.

Strict confidentiality will be maintained. Clinical records will be stored in a restricted location and only the research team and clinical staff assigned to the care of the individual subjects will have access to the records. An exception to this rule will be made for representatives of the FDA and the National Institute on Drug Abuse (NIDA) and contract monitors and or auditors. The subject will be informed of these exceptions in the informed consent document.

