4.4 Early Withdrawal of Subjects

4.4.1 When and How to Withdraw Subjects

Clinical Trial Discontinuation Criteria: All randomized subjects are included in the intent-to-treat analysis. All subjects who prematurely discontinue treatment will be scheduled for a final evaluation, the end-of-trial visit. Subjects will also be given appropriate treatment referrals. Subjects are not dropped from all study activity unless they request they not be contacted, or the subject cannot be located for assessment. Subjects will be informed at the consent session that medications may be discontinued due to: 1) Intolerable side effects; or 2) Extreme lab values with a repeat test. In these two cases, the subjects may continue with the CBT part of the treatment, as well as receive medical attention. Subjects will be informed at the consent session that he or she may be discontinued from all treatment due to: 1) Development or exacerbation of significant psychiatric or medical symptoms that necessitate inpatient admission or a more aggressive therapeutic intervention than provided by the protocol; these subjects would not be invited back to take study medication but will be followed for data collection and may remain eligible for psychosocial treatment; 2) A return to significant cocaine use or emergence of another substance abuse problem which necessitates inpatient admission or a more aggressive treatment than provided by the protocol; subjects who are admitted for inpatient stabilization for cocaine use may return for data collection and psychosocial treatment after discharge to complete the 12 week trial, but study medication will not be restarted if they miss more than two weeks of study medication; 3) Incarceration > 1 week; subjects may return for data collection and psychosocial treatment after discharge to complete the 12 week trial but study medication will not be restarted if they miss more than two weeks of study medication 4) subject's behavior compromises subject's safety. The reason the subjects are discontinued from medication and/or the clinical trial and any referrals made are documented in a Note to File found in the subject's source document binder or medical chart. Study medications will not be restarted in subjects missing more than two weeks of study medications because this would necessitate restarting the dose titration schedule and may result in

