There have been no severe interactions noted between varenicline and any other drugs. Nonetheless, in the proposed study, weekly monitoring by a nurse or physician provides a safety net. We will be monitoring adverse events via self-reports, BAC readings, and liver enzymes collected routinely during the trials. Side effects can be treated by lowering the dose of study medications or discontinuing the study medications when necessary. The subject will be discontinued from medications if he or she has experienced a medication associated serious adverse event (SAE), cannot tolerate minimum dosages of study medication, or becomes pregnant. Any subject who is discontinued from the study medications can still complete the CBT portion of the treatment. If the subject reports an SAE, the subject will be followed until the event is resolved. Federal, sponsor, and institutional guidelines are followed for reporting SAEs.

Clinical Deterioration and/or Suicide Risk Management: All of the investigators have had experience managing and referring subjects under these conditions. We follow the TRC's standing emergency policy when managing clinical deterioration related to addiction or psychiatric symptomatology for all of our subjects. At the weekly visit, subjects are evaluated for the presence or persistence of any symptoms indicative of clinical deterioration due to a rapidly increasing problem with cocaine use, drinking, and/or psychiatric symptoms, including suicidality. Between visits, subjects are instructed to contact their treating physician or an authorized research staff member in the event that disturbing symptoms become evident. In all cases, these subjects are immediately evaluated, and if deemed appropriate, are referred to clinical treatment. If possible, they will be maintained in the trial as long as all it is deemed safe to do so. Also, any additional treatment is recorded for data analysis purposes. At any time, subjects who are severely suicidal or at high risk of medical or physical harm will be immediately discontinued from the trial. All subjects who are discontinued from the trial are still encouraged to attend the end of treatment visit.

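### Sections 5.2 and 1.3 end a subject's trial participation where section 4.4.1 keeps data collection going, so primary-outcome data can stop for reasons linked to the drug or the outcome

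*Combined protocol and SAP*

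**What the plan says.** Two places end participation in the trial, as distinct from study medication:

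- Section 5.2, in the paragraph on clinical deterioration and suicide risk: "At any time, subjects who are severely suicidal or at high risk of medical or physical harm will be immediately discontinued from the trial". What remains for these subjects is one optional contact: "All subjects who are discontinued from the trial are still encouraged to attend the end of treatment visit".
- Section 1.3, Protection of Subjects, lists the possible responses to an adverse event. They finish with "a temporary cessation of study drug, or early termination from the trial, if necessary".

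Section 4.4.1 takes a different line. Its general rule is: "Subjects are not dropped from all study activity unless they request they not be contacted, or the subject cannot be located for assessment". For subjects stopped because of significant psychiatric or medical symptoms it adds: "these subjects would not be invited back to take study medication but will be followed for data collection".

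A lesser discrepancy concerns section 1.3, Consent Procedures. Subjects are given this notice: "their participation in the treatment trial may be discontinued at any time because of serious medication side effects, their noncompliance with treatment, missing appointments". Danger to their welfare is a further ground. Section 4.4.1 lists neither noncompliance nor missed appointments as a reason, and section 5.5 answers poor medication compliance with counseling.

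**The concern.** A severely suicidal subject, or one at high medical risk, can meet the section 5.2 criterion and the psychiatric or medical criterion of section 4.4.1 at once. Staff who follow 5.2 could reasonably stop the three-times-weekly urine and TLFB. Staff who follow 4.4.1 would continue them. The protocol does not say which applies.

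This matters because the main analysis is intent-to-treat on all randomized subjects and uses daily use indicators built from urine and TLFB (sections 4.4.1 and 7.2). The reasons for stopping are not neutral. Neuropsychiatric events are the subject of the boxed warning reproduced in section 1.3, so stops may be unequal by arm. The deterioration assessed in section 5.2 also includes rapidly worsening cocaine use, which is close to the outcome itself. Section 7.2 already concedes that ignorable missingness is implausible. Its drop-out model uses baseline characteristics and earlier responses, not the reason for stopping.

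**Working it through.** **1. Is this only loose wording?** The protocol separates stopping medication from stopping the trial in several places:

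- Section 5.2 lists reasons to come off study medication, with CBT still available, and then separately describes discontinuation from the trial.
- Section 1.3 names dose reduction, temporary drug cessation and early termination from the trial as distinct steps.
- Section 4.4.1 requires documentation of the reason for stopping medication, the clinical trial, or both.
- Section 6 brings the end-of-medication evaluation forward for participants discontinued early from the trial.

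So the word trial in 5.2 cannot simply be read as medication.

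**2. Follow-up by reason.**

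| Reason | Where | Data collection afterwards |
|---|---|---|
| Severe suicidality, high risk of harm | 5.2 | Final visit encouraged |
| Adverse event leading to termination | 1.3 | Not stated |
| Psychiatric or medical symptoms | 4.4.1 | Continues |
| Inpatient stay for cocaine use; incarceration | 4.4.1 | Subject may return for it |
| Intolerable side effects, extreme lab values | 4.4.1 | Only CBT and medical attention mentioned |
| Unsafe behavior | 4.4.1 | Nothing specific |

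The general retention rule of 4.4.1 covers the last three rows by implication, but the wording differs from row to row.

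**3. What a stop costs one subject.** Visits 4 to 39 give 3 × 12 = 36 scheduled medication-phase urines. If collection ended after medication week 3, 6 or 9, the loss would be 36 − 9 = 27, 36 − 18 = 18 or 36 − 27 = 9 urines (75%, 50% or 25%).

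**4. Possible bias.** Section 7.1 states no power, effect size, use rate or dropout allowance, so there is no plan figure to reproduce. All inputs here are assumed: use p = 0.60 while observed in both arms; stops at mid-phase, so half the phase is lost; true use q after the stop between 0.60 and 1.00; shares stopped sV (varenicline) and sP (placebo). Differences are in use rate, varenicline minus placebo.

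- True difference = (sV − sP) × 0.5 × (q − 0.60)
- Available-case difference = 0, because both arms show 0.60 while observed
- Missing-as-positive difference = (sV − sP) × 0.5 × (1 − 0.60)

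| sV vs sP | True difference, q = 0.60 to 1.00 | Available case | Missing as positive |
|---|---|---|---|
| 10% vs 5% | 0 to 0.05 × 0.5 × 0.40 = 1.0 point | 0 | 1.0 point |
| 15% vs 5%, or 20% vs 10% | 0 to 0.10 × 0.5 × 0.40 = 2.0 points | 0 | 2.0 points |

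Each analysis can be wrong by 0 to 2 points, in opposite directions: available-case understates varenicline use and missing-as-positive overstates it. If placebo subjects are stopped more often (5% vs 15%), the signs reverse. With equal stopping in this setup there is no bias.

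**5. Scale.** With 100 per arm, 80% power and two-sided alpha 0.05 (the plan gives 0.05 but not the sidedness), the detectable standardized difference is (1.96 + 0.84) × √(2/100) = 0.40. For a simple comparison of proportions from base rates of 20% to 50%, it is about 18 to 20 points. The repeated-measures model will differ, but a shift of 0 to 2 points is small on this scale.

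**The case against.** The best defense is that the sections can be read together. No section says that urine or TLFB collection ends. The retention rule in 4.4.1 covers every reason and sits in the section on how to withdraw subjects, which itself mentions discontinuation from the clinical trial. Section 5.2 makes keeping subjects in the trial the default where that is possible and safe, so the immediate stop is a narrow exception. Section 4.4.2 sets out persistent re-contact. An attended final visit can recover self-report, because the TLFB covers the time since the last visit. Known serious adverse events are followed to resolution in any case. Stops may also be few: section 1.3 reports no medication-associated serious adverse events among 77 pilot subjects, and current suicidal ideation is an exclusion.

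Most of this stands, and it limits the point. A reader might infer that the protocol orders outcome collection to cease, or that the primary comparison will be materially biased. The documents support neither: the first is an inference from the wording, and the second depends entirely on assumed rates. A reader might also infer that subjects will be removed for noncompliance or missed visits. The consent text is only permissive, and its phrase about the treatment trial may mean treatment alone. Nor can sites diverge, since the trial has one center; any inconsistency would be between staff members or over time.

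What the defense does not remove is that two instructions apply to the same subject and only one of them states that data collection continues. Re-contact procedures and a final visit do not restore the repeated urines. Section 7.2 itself says that assumptions about drop-out cannot be tested on the observed data.

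**Conclusion.** The contradiction between sections 5.2 and 1.3 and section 4.4.1 is real, and it bears on collection of the primary outcome. It can create non-ignorable missingness linked to the drug or to cocaine use, some of it avoidable by clearer wording. The severity is moderate. The documents give no stopping rates, so the bias cannot be computed; the 0 to 2 points rest wholly on the assumptions shown and would grow only if stopping were common or very unequal by arm. The conclusion rests on the conflicting instructions rather than on a large calculated effect. The consent wording on noncompliance and missed appointments is a secondary matter of consistency.

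**What to change.** Reconcile section 5.2 and both paragraphs of section 1.3 with section 4.4.1 on one question only: which outcome data (urine, TLFB, adverse-event contact) are still sought after each type of stop. State the answer in the same terms for every reason in 4.4.1, consistent with its general retention rule and the contact procedures of 4.4.2, subject to consent and to the subject being safely able to take part. Say in the consent text whether noncompliance or missed appointments affect data collection.

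Section 4.4.1 already has the reason for stopping written in a Note to File. Record it also as a coded data field and name it in section 7.2 for use in the missing-data sensitivity analyses.

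The criteria for stopping treatment or participation, and clinical management after a stop, are not part of this request and stay with the clinicians.

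The cost is a protocol and consent wording amendment, one coded field, and some extra visits and payments for discontinued subjects. Some subjects will still be unable to attend, so the change reduces the missing data but does not eliminate it.

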5.3 Method for Assigning Subjects to Treatment Groups

Urn Randomization: We will use urn randomization to stratify subjects across the two experimental conditions. In the randomization scheme, we will stratify subjects on 2 baseline variables: 1. Gender; 2. Cigarette smoking status. We have no reason to suspect gender differences to mediate outcomes; however, it certainly is possible, given our sparse knowledge about female alcohol and drug abusers. Also, because we estimate that fewer than 30% of our final sample will be females, based on TRC census data over the past 5 years, it is imperative that we use gender as one of the urn variables in randomizing.

5.4 Preparation and Administration of Study Drug

Study medication will be prepared, stored and dispensed by the Research Pharmacist at the Hospital of the University of Pennsylvania. [name] can be contacted at [contact].

5.5 Subject Compliance Monitoring

Medication Adherence: Medication adherence will be monitored via observed dosing at each study visit and by pill counts upon the weekly return of the blister card. These will also serve as the basis for actively enhancing medication adherence done as part of Combine's Medical Management procedures. Blister cards can be organized by row and column and clearly marked per daily dose. The design of the HUP blister cards makes it easy to titrate the dosage up at the initiation of the trial. Blister packs provide the subjects with easy access for viewing the number of pills missing vs. remaining for each day since each pill is individually packaged and daily dosages are clearly marked. Subjects will be given one blister card each week and are asked to bring it with them at each study visit and to return it the following week. Each blister card contains the dose per day for each of the seven days of the week. Doses for a given day are designated in a single row, with rows numbered consecutively to represent the days of the week.

We purposely chose not to use the Medication Event Monitoring system (MEMs) cap bottles to dispense medications in this study due to their prohibitive costs. We chose not to use a riboflavin marker to measure adherence because riboflavin has been shown to be an unreliable indicator of compliance due to difficulty in determining visual thresholds for the presence/absence of riboflavin. Therefore, we will use pill counts in the presence of a returned blister pack to secondarily assess medication adherence. We reimburse the participant \$5 for each blister card returned, empty or not. We have been doing this for over 5 years, with our IRB's approval. This procedure has netted us 80-90% return of blister cards by our research participants.

Subjects who are significantly noncompliant with treatment medication (indicated by less than 50% of doses taken) will be counseled by the nurse assigned to MM therapy. If that does not result in improved medication compliance, these subjects will meet with the PI of the study for further counseling.

5.6 Prior and Concomitant Therapy

Concomitant medications will be recorded for 30 days prior to consent throughout the end of treatment phase. Medications that will not be allowed during screening week and the randomization phase include antidepressants, antianxiety medications, antipsychotic medications,

naltrexone, disulfiram, modafinil, stimulants, anticonvulsants, benzodiazepines, haloperidol. Anticonvulsants (e.g., gabapentin) prescribed for pain will not be exclusionary.

Additional psychosocial therapies, including self-help groups, will be allowed during the randomized medication phase, but will be measured using the Treatment Services Review (TSR). Subjects admitted to inpatient detoxification during the trial may be invited back to continue psychosocial treatment and medications as outlined in section 1.1.2 above.

5.7 *Packaging*

Study drug will be dispensed weekly. It will be dispensed in blister packs with each daily dose clearly marked. Blister packs will be labeled with the name and address of the research Pharmacy, the name and 24 hour phone number of the PI, subject initials, randomization number, name of the study drug, study week, and # of capsules and instructions. Each row on the blister pack represents a day's dose, with the two daily doses clearly identified.

5.8 *Receiving, Storage, Dispensing and Return*

5.8.1 *Receipt of Drug Supplies*

Study drug is to be supplied by Pfizer or purchased and will be over-encapsulated by the Research Pharmacy at the Hospital of the University of Pennsylvania. The matching placebo will be produced and over-encapsulated by the Research Pharmacy at the Hospital of the University. All study medication will be stored and dispensed by the Research Pharmacy at the Hospital of the University of Pennsylvania.

5.8.2 *Storage*

Study medication will be stored at the Research Pharmacy at the Hospital of the University of Pennsylvania. A portion of the packaged medication will be stored on-site in a locked cabinet in order to be available for participants in the treatment phase of the study. Per FDA guidelines, all study medication both on-site and at the pharmacy will be stored at 25°C (77°F) with excursions permitted to 15-30°C (59-86°F).

5.8.3 *Dispensing of Study Drug*

After randomization, study drug will be dispensed to each subject according to his or her randomization number. Medication will be dispensed by blister pack each week. A pill count log will be maintained in each subject's CRF indicating how many capsules were dispensed and how many collected at the end of the week. A dispensing log will also be maintained at the Research Pharmacy.

Regular study drug reconciliation will be performed to document drug assigned, drug consumed, and drug remaining. This reconciliation will be logged on the drug reconciliation form, and signed and dated by the study team.

5.8.4 *Return or Destruction of Study Drug*

All unused study drug will be returned to the Research Pharmacy. At the completion of the study, there will be a final reconciliation of drug obtained from the Research Pharmacy, drug consumed, and drug returned. This reconciliation will be logged on the drug reconciliation form, signed and

dated. Any discrepancies noted will be investigated, resolved, and documented prior to return or destruction of unused study drug. Drug destroyed on site will be documented in the study files.

6 Study Procedures

DESCRIPTION OF INSTRUMENTS (in alphabetical order)

1. **Addiction Severity Index** (ASI) (McLellan et al., 1992). The ASI is a 45-minute interview which yields composite scores, ranging from 0 to 1, of problem severity over the past 30 days in 7 areas: medical, employment, drug use, alcohol use, legal, family/social, and psychiatric. Studies have shown moderate to excellent interrater and test-retest reliability. The ASI will be used to characterize baseline demographic and drug use variables for each subject. The composite scores will be used as secondary outcome measures. The ASI is administered research staff at Baseline, at Week 7 and at medication completion (Visit 40).
2. **Adverse Events** (AE) Adverse events will be collected at every visit and recorded in the CRF. Severity, expectedness, relatedness to study drug, action taken, and outcome will all be recorded (Visits 1-40).
3. **Brief Substance Craving Scale** (BSCS) (Somoza et al 1995). This instrument is to be used to assess craving once weekly. The instrument was designed by the Craving Subcommittee of the NIDA Medications Development Research Units (MDRU). It is an expansion of the Cincinnati Craving Scale. Reliability data for the intensity and frequency questions has been collected at the Cincinnati MDRU. The questions regarding Length, Number and Time were added by the Subcommittee. The BSCS will be administered weekly and at the end of the randomized medication phase (Visits 1, 4, 7, 10, 13, 16, 19, 22, 25, 28, 31, 34, 37, 40)
4. **Clinical Global Impression Scale** (CGI) (Guy, 1976). The CGI is a brief clinical rating of severity of illness (at time of interview) and global improvement (from admission) using a 7-point Likert scale. The CGI is done by an observer (CGIO) and the subject (CGIS) to assess clinical progress, global improvement and to assess the severity of the subject's illness at regular contacts over the course of the study. The CGI is done once during baseline by the observer and subject, weekly during the medication phase of the trial by the observer and subject and once at the end of randomized medication phase by the nurse or physician and subject, (Visits 1, 4, 7, 10, 13, 16, 19, 22, 25, 28, 31, 34, 37, 40).
5. **Clinical Institutes Withdrawal Assessment for Alcohol, Revised** (CIWA-AR) (Sullivan and Sellers 1989). The CIWA-AR is a valid and reliable measure of alcohol withdrawal symptom severity. It will be used to verify the need for alcohol detoxification prior to randomization and to measure alcohol withdrawal symptom severity among subjects who relapse to alcohol use during the trial. The CIWA-AR will be administered at least once during the baseline.
6. **Cocaine Craving Questionnaire** (CCQ) (Tiffany et al. 1993) This instrument will be administered once weekly, and at the end of randomized medication phase, to specifically assess cocaine craving (Visits 1, 4, 7, 10, 13, 16, 19, 22, 25, 28, 31, 34, 37, 40).
7. **Cocaine Selective Severity Assessment** (CSSA) (Kampman et al., 1998). The CSSA is a 10-minute, 18-item study personnel-administered cocaine withdrawal scale developed at the TRC. The scale measures items that commonly occur after abrupt cessation of cocaine use, including: cocaine craving, depressed mood, appetite changes, sleep disturbances, lethargy, and bradycardia. Individual items are scored on a 0-7 scale and a total score is derived from a sum

of the individual item scores. The CSSA has been found to be a reliable and valid measure of cocaine withdrawal symptoms. The CSSA will be administered by research staff at each visit during baseline, weekly during the medication phase of the trial and at the end of randomized medication phase (Visits 1, 2, 3, 4, 7, 10, 13, 16, 19, 22, 25, 28, 31, 34, 37, 40).

8. **Concomitant Medications** (CONMEDS) Concomitant medications will be recorded starting from 30 days prior to consent to the end of the randomized medication phase. They will be recorded weekly by the study nurse or physician, once at the end of randomized medication phase, and once at end of treatment (Visits 1, 4, 7, 10, 13, 16, 19, 22, 25, 28, 31, 34, 37, 40).
9. **Delay Discounting Questionnaire** (Kirby & Marakovic, 1996) This questionnaire asks participants to repeatedly choose between two hypothetical monetary rewards: immediately available (smaller sooner rewards) and temporally delayed for time period between 10 and 75 days (larger later). The questionnaire allows for calculation of an indifference point, which is the value at which a participant switches from preferring the smaller sooner to the larger later reward. This indifference point is a measure of impulsivity, and can be tracked through repeated administration of the Delay Discounting questionnaire to assess changes in impulsivity over time (Visits 1, 4, 7, 10, 13, 16, 19, 22, 25, 28, 31, 34, 37, 40).
10. **Fagerstrom Nicotine Tolerance Questionnaire** (FNTQ 25) is a 5-minute, 8-item, self-report designed to measure physical dependence to nicotine. The validity and reliability of this scale have been supported in numerous studies. Scores range from 0 (no dependence) to 11 (high dependence). A score of 8 or more is considered to be indication of high dependence and 4-7 moderate dependence. This questionnaire will be administered once in the screening weeks (Visit 1).
11. **Medical history & Physical exam (PE)** A complete medical history and physical exam will be conducted by the nurse or physician at Visit 1. The physical exam will be repeated at visit 40.
12. **Minnesota Cocaine Craving Scale** (MCCS) (Halikas et al., 1991). The MCCS is a valid and reliable measure of cocaine craving. Craving is assessed over three dimensions, intensity, duration, and frequency and subjects are asked to evaluate their craving for the prior week. The MCCS will be administered at baseline, weekly throughout the medication phase of the trial, once at the end of randomized medication phase (Visits 1, 4, 7, 10, 13, 16, 19, 22, 25, 28, 31, 34, 37, 40).
13. **Multiple Choice Procedure (MCP)** (Griffiths, Troisi II, Silverman & Mumford, 1993) This adaptation of the MCP asks participants to choose between a hypothetical static amount of cocaine and hypothetical variable amounts of money. Repeated administrations of the MCP allow for assessment of changes in the relative reinforcing effects of cocaine over time, evidenced by shifts in how much participants are willing to “pay” for a static amount of cocaine (visits 1, 4, 7, 10, 13, 16, 19, 22, 25, 28, 31, 34, 37, 40).
14. **Pill Count** The number of capsules of study medication dispensed and the number returned each week will be recorded in the CRF (visit 4, 7, 10, 13, 16, 19, 22, 25, 28, 31, 34, 37, 40).
15. **Structured Clinical Interview for DSM-IV (SCID) (First et al., 1996), Mini-International Neuropsychiatric Interview (MINI) (Sheehan et al., 2002)** The substance abuse module (Module E) of the SCID-IV will be used to diagnose substance abuse problems. The major depressive episode modules (Modules A and B) of the MINI Plus will be used to diagnosis current and past episodes of major depression and current episodes of major depression with melancholic features. Other lifetime DSM-IV Axis I and II diagnoses will be obtained from the MINI. The SCID/MINI/MINI Plus will be done once during baseline to confirm diagnoses

of cocaine and alcohol dependence and determine if Axis I, Axis II or other substance disorder diagnoses are present. Time of administration will be 45 minutes. The SCID/MINI/MINI Plus will be administered by a clinically-trained Diagnostic Interviewer.

16. **Timeline Follow Back Interview** (TLFB) (Sobell and Sobell, 1995). The TLFB is a 15-30 minute, semi-structured interview adapted by our laboratory to collect information about daily cocaine, alcohol, and nicotine use. Critical life events are reviewed retrospectively to prompt recall of cocaine use measured in days used and dollars worth of cocaine used. Nicotine use is measured by number of cigarettes (or other forms of tobacco) per day. Cocaine, and nicotine use are recorded on a personalized calendar. Other drugs and any days spent in a controlled environment are also recorded on the calendar. The TLFB will be given by trained research staff at baseline to cover 3 months immediately preceding treatment entry and will be updated at each research visit to determine any time spent in a controlled environment and cocaine, nicotine, and other drug use during the period since the last visit. The composite of these assessments will be additive over the course of the study so that we will have continuous data on cocaine and nicotine use (Visit 1 through 40).
17. **Treatment Group Prediction Form** Integrity of the study blind will be evaluated by having the nurse or physician, therapist, research staff and subject predict which medication group assignment (active or placebo). (Week 7 and Visit 40).
18. **Treatment Services Review** (TSR) (McLellan et al., 1992). The TSR is a 5-minute interview given by the research staff to record the subject's use of services received in 7 areas covered in the ASI since the last visit. Test-retest reliabilities are high (McLellan et al., 1992a). The measure is given during baseline week, weekly throughout the medication phase, at the end of randomized medication phase and at the end of treatment visit so that there is a continuous record of non-study treatment services throughout the trial (Visits 1,4,7,10,13,16,19,22,25,28, 31, 34, 37, 40). These data will be used to compare utilization of ancillary treatments during the trial in the varenicline and placebo groups.
19. **The Symptom Checklist 90 Revised** (SCL-90-R) (Derogatis, 1977) is a ninety item self report measure that measures psychiatric symptom severity on a 4 point scale from 0 "not at all" to 4 "extremely." Nine factor scores are generated including depression, anxiety, phobic anxiety, somatization, interpersonal sensitivity, paranoia, psychotism, obsessive-compulsive, and hostility. This scale is a standard measure used clinically at the Treatment Research Center. It has been shown to correlate well with clinician rated improvement and provides a measure of self-perceived symptom reduction. It will be administered at baseline and the end of the randomized medication phase (Visits 1 and 40).
20. **Risk Assessment Battery** (RAB) (Snider et al., 1994) is a 38 item self report questionnaire which assesses high risk behavior for exposure to the HIV virus. The RAB yields drug, sex and total risk scores. It will be administered at baseline and the end of the randomized medication phase (Visits 1 and 40).
21. **Hamilton Anxiety Rating Scale** (Ham A) This instrument will be administered during baseline and at the end of the randomized medication phase (Visits 1 and 40) to assess changes in anxiety symptoms that occur during the trial.
22. **Hamilton Depression Rating Scale** (Ham D) (Nordgren 1995, Hamilton 1967). This instrument will be administered during baseline and again at the end of treatment to assess changes in depressive symptoms. This version of the Hamilton Depression Scale is based on the Hamilton Rating Scale for Depression (HRSD-24). Items 25 through 28 (Increased Appetite, Weight Gain, Hypersomnia, Social Withdrawal) have been added by the NIDA

Medications Development Division from various other scales believed to be pertinent to MDD research. These have not been validated. The additional items will be analyzed separately. This instrument will be administered at baseline and at the end of the randomized medication phase (Visits 1 and 40).

23. **Short Form-36 Health Status Questionnaire** (SF-36) (Jenkinson, 1994). The SF-36 is a 10-minute, 36-item self-report of the subject's quality of life. Eight health concepts are assessed: 1) limitations in physical activities; 2) limitations in social activities due to physical or emotional problems; 3) limitations in activities due to physical problems; 4) bodily pain; 5) general mental health; 6) limitations in activities due to emotional problems; 7) vitality; and 8) general health perceptions. The SF-36 will be given once at baseline, at end of treatment (week 14).
24. **Weight and Vital Signs** Body weight, temperature, pulse and blood pressure will be monitored weekly, and at the end of randomized medication phase (Visits 1, 4, 7, 10, 13, 16, 19, 22, 25, 28, 31, 34, 37, 40).

Laboratory Measurements

1. **Breathalyzer** (BAL) Blood alcohol levels will be estimated at each study visit (1-40) by breathalyzer.
2. **Carbon Monoxide** (CO) Expired carbon monoxide, a biomarker for very recent cigarette smoking will be assessed at each visit (1-40) by Bedfont CO monitor.
3. **Urine cotinine** will be measured at each study visit (1-40) using NicCheck urinary cotinine dipstick testing. Cotinine captures cigarette smoking within the past 48 hours.
4. **Electrocardiogram** is a standard 12-lead ECG recorded once during baseline and one time at the end of randomized medication phase by the nurse or physician. Any abnormal results are brought to the attention of the principal investigator or study physician (Visits 1, 40).
5. **Complete Blood Count and Blood Chemistry** will be collected once at baseline and once at the end of the randomized medication phase by the nurse or physician and sent to an off-site laboratory for examination. The tests include glucose, uric acid, BUN, creatinine, glom filt rate, BUN/creatinine ratio, sodium, potassium, osmolality, albumin, bilirubin, alkaline phosphatase, LDH, AST (SGOT), ALT (SGPT), GGT, cholesterol, triglycerides, HDL cholesterol, VLDL cholesterol, LDL cholesterol, T. cholesterol/HDL ratio, Estimated CHD risk, WBC, RBC, hemoglobin, hematocrit, MCV, MCH, MCHC, RDW and platelets. Any abnormal results are brought to the attention of the principal investigator or study physician (Visits 1 and 40).
